4.5.4 Subgroup Analyses

The TICI will be compared between the baloxavir marboxil plus SOC NAI and matching placebo plus SOC NAI arms for the following subgroups:

- region
 - North America (United States, Canada);
 - Europe, Middle East, and Africa [EMEA] (Belgium, Bulgaria, Czech Republic, Estonia, France, Germany, Hungary, Israel, Netherlands, Romania, Serbia, Spain, Sweden, Turkey, Ukraine);
 - Rest of world [ROW] (Mexico, Japan, South Korea, Brazil, Argentina, Peru, Australia, New Zealand, Hong Kong, Singapore, China)
- baseline age (<65, ≥65 years)
- baseline age (<80, ≥80 years)
- baseline NEWS2 score (≤7, >7)
- time from symptom onset to study treatment (≤48 hours, >48 hours)
- ICU or mechanical (invasive/non-invasive mechanical or ECMO) intervention at baseline or any point during the study prior to clinical improvement (Yes, No)
- Patients who received anti-influenza drug within 48 hours prior to screening (including Oseltamivir, Zanamivir, Peramivir, Laninamivir, Arbidol, Favipiravir, Amantadine, Rimantadine) (Yes, No)
- On-treatment NAI (Oseltamivir, Zanamivir, Peramivir)
- Immunocompromised patients (Yes, No) – see [Appendix 6](#)
- Patients with ongoing comorbidities at baseline
 - Respiratory comorbidities:
 - Pneumonia (Yes, No). Including any event preferred term with “pneumonia”.
 - Respiratory thoracic and mediastinal disorders System Organ Class and/or pneumonia (Yes/ No)
 - Respiratory influenza complications that required or extended hospitalization, defined as required ventilation or supplemental oxygen and/or complications of ‘respiratory’ class as assessed by the investigator
 - Cardiac comorbidities
 - Cardiac disorders System Organ Class

- Cardiac influenza complications that required or extended hospitalization, defined as complications of ‘Cardiac’ class as assessed by the investigator
- Patients contracting nosocomial influenza (e.g. prolonged hospitalization)
- influenza subtype (A, B) at baseline– will be conducted if >10% patients in B
- virus subtype (H1, H3) at baseline
- presence of co-respiratory infection at baseline (identified via the non-influenza respiratory bacterial and virus co-infection panel) (Yes, No)
- high and low baseline viral titre e.g. 2 groups split at the median
- high and low viral titre AUC e.g. 2 groups split at the median

Subgroups will be analyzed descriptively. The median TTCl for each subgroup and a 95% CI will be presented.

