4.6.1 Exploratory Endpoints

Polymorphic and treatment-emergent amino acid substitutions in the PA, PB1, PB2, and NA genes

Sanger sequencing of PA and NA will be performed for all or neuraminidase treated patients, respectively, and with paired (pre and post dose) samples available, at baseline and at the last evaluable timepoint (last sample with $> 4 \log_{10}$ viral particles/ml). For patients with amino acid substitutions in the PA gene, additional sequencing will be performed for all earlier timepoint samples to evaluate the timepoint of emergence of the amino acid substitution. In addition, sequencing of PB1 and PB2 genes will be performed on samples selected based on the criteria below. The number and proportion of patients with the detected amino acid substitutions will be reported for all investigated genes.

Sequencing of PB1 and PB2 will be done for:

- baseline viruses with reduced susceptibility to baloxavir (fold-change in $EC_{50} > 10$ for type A viruses and > 5 for type B viruses compared to reference virus in phenotypic assay).
- viruses (baseline and last evaluable time-point) without amino acid substitution in PA, but with reduced response to treatment or with virus rebound.

These will be defined according to the following criteria below in [Table 13](#). If an amino acid substitution is detected, an additional intermediate time point sample will be sequenced.

Table 13 PB1 and PB2 Sequencing

	Criteria
1) Subjects who exhibit viral titer rebound:	Viral titer at [(a certain time point) – (just before time point)] \geq 2 x SD value of viral titer of control virus in assay * * [REDACTED]
2) Subjects who continue to shed virus at Day 6 and beyond:	Viral titer (log ₁₀ TCID ₅₀ /mL) at Day 6 and beyond > 1.5
3) Subjects who do not show a reduction in virus titer:	Viral titer (log ₁₀ TCID ₅₀ /mL) at a certain time point: A > 1.5 Viral titer (log ₁₀ TCID ₅₀ /mL) at just before time point: B > 1.5 AND Viral titer (log ₁₀ TCID ₅₀ /mL) at [(a certain time point: A) - (just before time point: B)] \geq 0

Drug susceptibility in patients with evaluable virus

As assessments of the drug susceptibility of the influenza virus, the 50% effective concentration (EC₅₀) of baloxavir or the 50% inhibitory concentration (IC₅₀) of neuraminidase inhibitor # (will be measured by the ViroSpot™ or NA-Star® assay, respectively, using baseline swab samples.

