4.6.2 Subgroup Analyses

Subgroup analysis of the following virology endpoints, based on virus type and subtype, will be conducted by treatment group:

- Time to cessation of viral shedding by RT-PCR
- Time to cessation of viral shedding by virus titer

For the baloxavir treatment group only, an additional subgroup analysis comparing the patients with or without the presence of virus with an I38x substitution will be conducted for the following:

- Time to cessation of viral shedding by RT-PCR
- Time to cessation of viral shedding by virus titer
- Number and % of patients having 2 doses of baloxavir; number of patients having 3 doses of baloxavir

Subgroup analyses will be produced where appropriate and where the number of patients in each subgroup is sufficient.

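### Two TTCI subgroups, viral titre AUC and on-study ICU/ventilation, are defined by post-randomisation data, so the arm contrasts within them are not protected by randomisation

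*SAP*

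**What the plan says.** SAP 4.5.4 compares TTCI between the baloxavir "plus SOC NAI and matching placebo plus SOC NAI arms for the following subgroups", giving a median and 95% CI for each. Most of the list is fixed before treatment (region, age, baseline NEWS2, baseline titre, influenza type). Two entries are not:

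- "high and low viral titre AUC e.g. 2 groups split at the median";
- ICU or mechanical (invasive, non-invasive or ECMO) "intervention at baseline or any point during the study prior to clinical improvement".

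The section adds that "Subgroups will be analyzed descriptively". It does not mark these two entries as post-randomisation, and it does not say whether the AUC median is taken over both arms or within each arm.

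Protocol 6.4 gives the purpose of the subgroups as checking that results are consistent. Its examples (age, sex, race/ethnicity, stratification factors, anti-influenza drugs before enrolment) are all pre-treatment. SAP 4.6 presents titre AUC by treatment group as an endpoint. Protocol 1.3 expects the combination to reduce viral load more than either component alone. Incidence of ICU stay and of mechanical ventilation are secondary endpoints (SAP 4.5.3).

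**The concern.** Randomisation makes the arms comparable within a subgroup only if membership cannot be changed by treatment. Titre AUC builds up over the scheduled swabs to Day 10, while the assumed control median TTCI is 94 h. So about half of the control patients would improve before their AUC is complete.

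If baloxavir lowers AUC, its moderately ill patients move from the high to the low group. The baloxavir patients left in the high group are the sickest, and the low group gains sicker patients than its placebo counterpart has. Baloxavir then looks worse in both groups with no difference overall.

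The ICU/ventilation group has a further problem. A patient can qualify at any time up to the outcome, so slow improvers have longer to be classed as Yes.

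These tables will stand beside genuine baseline subgroups, with the same layout and intervals. A drug that clears virus could appear harmful in every AUC stratum, and a reader could take that as evidence against consistency of effect.

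**Working it through.** **1. Yardstick.** The plan gives no figure for subgroup bias, so its design effect is the yardstick. SAP 2.4 assumes 94 h on placebo and a 31 h difference, so 63 h on baloxavir and a ratio of 94/63 = 1.492. The mITTI size is 366 × 0.75 × 0.96 = 263.5, about 264. By 840 h nearly all patients have an event (1 − 2^(−840/94) = 0.998). A fixed design gives z = ln(1.492) × √(264 × 2/9) − 1.96 = 1.10, or 86.5% power. With the futility rule followed at 65% of events, power is 80.3% and the bound is one-sided p = 0.077. Both agree with the SAP.

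**2. AUC model.** Severity S is standard normal. AUC = 0.7·S + √0.51·noise − d on baloxavir. TTCI is exponential with log-mean c + b·S, where c sets the median at 94 h in **both** arms. Allocation is 2:1, there is no censoring, and the split is at the pooled median. The correlation of AUC with log TTCI is 0.7b/√(b² + π²/6): 0.16 for b = 0.3 and 0.30 for b = 0.6. The documents give neither b nor d; both are assumptions.

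| b (corr.) | d, SD | In high group, balox. / placebo | High AUC, median h | Diff. | Low AUC, median h | Diff. |
|---|---|---|---|---|---|---|
| 0.3 (0.16) | 0.5 | 43% / 63% | 114.3 vs 106.8 | +8 | 81.5 vs 76.2 | +5 |
| 0.3 (0.16) | 1.0 | 37% / 75% | 116.7 vs 102.8 | +14 | 83.1 vs 72.3 | +11 |
| 0.6 (0.30) | 0.5 | 43% / 63% | 139.0 vs 121.8 | +17 | 71.1 vs 62.1 | +9 |
| 0.6 (0.30) | 1.0 | 37% / 75% | 145.5 vs 112.6 | +33 | 73.8 vs 55.9 | +18 |

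All differences are baloxavir minus placebo. With d = 0, or with each arm split at its own median, they are 0 within simulation noise.

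**3. Cross-check with another model.** Here TTCI is a plain exponential with median 94 h in both arms, linked to AUC by a Gaussian copula with correlation ρ. At ρ = 0.2, d = 0.5 the differences are +7.9 h (high) and +6.1 h (low). At ρ = 0.3 they are +11.6/+8.7 h for d = 0.5 and +22.4/+16.2 h for d = 1. The direction and order of size are the same.

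**4. ICU/ventilation.** Assume exponential TTCI with hazard λ = ln 2/94 = 0.00737 per hour in both arms, and an ICU/ventilation hazard μ = 0.0015 per hour on placebo (assumed). The share classed as Yes is μ/(λ + μ), and the median TTCI among the No group is ln 2/(λ + μ).

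- Same μ in both arms: 16.9% Yes and a No median of 78 h in each arm. The between-arm difference is 0.
- Baloxavir halves μ, no TTCI effect: 9.2% Yes, and the No median is ln 2/0.00812 = 85 h, so about +7 h. By simulation the Yes group differs by +8.3 h. With a shared frailty of SD 0.5 the differences are +32.8 h (Yes) and +8.9 h (No).
- Same μ, true TTCI effect (λ = ln 2/63 = 0.0110 on baloxavir): Yes shares are 12.0% vs 16.9%, and the No medians are 55.4 vs 78.1 h. The true 31 h difference shows as 22.7 h.

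Yes and No medians differ by 130 to 210 h in the simulations with no TTCI effect, including those where treatment does nothing. That gap comes from the outcome's own clock.

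**The case against.** The strongest defence is that these subgroups are descriptive, carry no test and lie outside the testing hierarchy. That is correct, and it limits the consequence. It removes the p-value but not the selection.

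A second defence is that the size depends on inputs the documents do not give. That also stands. The range above is illustrative, and a within-arm split would remove the bias in the shift model. The SAP does not specify such a split. If treatment did more than shift AUC equally for everyone, equal ranks in the two arms need not mean comparable patients.

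Three stronger readings are tempting and are not supported:

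- *The contrasts are biased even if the drug does nothing.* They are not. If treatment moves neither the marker nor TTCI, the between-arm bias is zero. Protocol 1.3 supports an effect on viral load, but an effect on ICU or ventilation is only a hypothesis under test.
- *Slow improvers having longer to qualify biases the arm contrast by itself.* It separates Yes from No, equally in both arms, unless treatment changes ICU/ventilation risk or TTCI.
- *The I38x analysis is a third biased arm comparison.* SAP 4.6.2 plans it "For the baloxavir treatment group only, an additional subgroup analysis comparing the patients with or without the presence of virus with an I38x substitution", on shedding time and number of doses. It has no placebo contrast and no TTCI, and it is worded as presence, not emergence. It is a separate, minor matter: a non-randomised comparison within one arm. Sequencing is "at baseline and at the last evaluable timepoint", and the last evaluable sample must exceed 4 log10 particles/mL. Emergent substitutions can therefore be found only in patients still shedding at that level after dosing.

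**Conclusion.** The point holds for the two TTCI subgroups. For titre AUC, the spurious difference is about 5 to 33 h against baloxavir in both strata. This assumes a 0.5 to 1 SD reduction in AUC, a correlation of about 0.16 to 0.3 between AUC and log TTCI, a pooled-median split and no effect on TTCI. It vanishes if treatment does not move AUC.

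For ICU/ventilation the bias is conditional. It needs a treatment effect on ICU/ventilation risk or on TTCI, and its size (about 7 to 33 h if the risk is halved with no TTCI effect) rests on an assumed event rate.

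The primary test, alpha, sample size and interim are not affected. What is at risk is the reading of these two tables as evidence that the effect is, or is not, consistent. The change is worth making because it is nearly free.

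**What to change.** In SAP 4.5.4:

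- Define the ICU/ventilation subgroup by status at baseline only, meaning the last record before first dose. ICU status at baseline is already summarised under SAP 4.3.3.
- Remove the titre-AUC split from the TTCI consistency subgroups, since baseline titre is already listed. Alternatively, report it in a separate exploratory section, labelled as post-randomisation and non-causal, with a statement of whether the median is pooled or set within each arm.

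As a minor companion edit in SAP 4.6.2, limit the I38x comparison to patients with paired sequences and state that it is a non-randomised description.

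The cost is SAP wording, with no new data. One descriptive table is lost or moved, and the baseline-only Yes group for ICU/ventilation will be smaller.

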4.6 VIROLOGY ENDPOINTS

The following virology endpoints will be analyzed for the mTTI population:

Time to cessation of viral shedding by virus titer

Time to cessation of viral shedding by virus titer is defined as the time, in hours, between the initiation of study treatment and first time when the influenza virus titer is below the limit of detection (0.75 log₁₀ TCID₅₀/mL) and will be analyzed using similar methods as specified for the primary endpoint (see Section 4.5.1).

Patients who are lost to follow-up, whose virus titers have not reached the limit by the last observation time point, or who die will be censored at their last observation time point or date of death, whichever is applicable, as per Table 12 below.

Table 12 Time to Viral Shedding and Censoring

Event	Censor	Date and Time
Death prior to cessation of viral shedding	Yes	last observation prior to death
Discontinuation for any reason prior to cessation of viral shedding	Yes	last observation prior to discontinuation
Lost to follow-up prior cessation of viral shedding	Yes	last observation
Virus titers have not reached the limit by the last observation time point	Yes	last observation

One day is converted into 24 hours. Patients with a positive virus titer on Day 1 will be included in this analysis.

Time to cessation of viral shedding by RT-PCR

Time to cessation of viral shedding by RT-PCR, in hours, is defined as the time between the initiation of study treatment and first time when the virus RNA by RT-PCR is below the limit of detection (2.05 for flu A and 2.83 for flu B \log_{10} virus particles/mL) and will be analysed using similar methods as specified for the primary endpoint (see Section 4.5.1).

Patients who are lost to follow-up, whose virus titers have not reached the limit by the last observation time point, or who die will be censored at their last observation time point or date of death, whichever is applicable, as per Table 12 above. For the patients with multiple virus types, this endpoint is defined as the time between the initiation of the study treatment and first time when the virus RNA by RT-PCR is below the limit of detection for all virus types. One day is converted into 24 hours.

Patients with a positive virus RNA on Day 1 will be included in this analysis.

Change from baseline in influenza virus titer at each timepoint

Change from baseline in influenza virus titer (\log_{10} TCID₅₀/mL) is defined as the change from baseline in influenza virus titer on Days 2, 3, 4, 5, 7, and 10 and will be analyzed using an analysis of covariance (ANCOVA) model with region (North America, EMEA, ROW), NEWS2 (≤ 7 , > 7), and time from symptom onset to study treatment (≤ 48 hours, > 48 hours) as stratification variables, and the baseline value as a covariate. If influenza virus titer is less than the lower limit of quantification, the virus titer will be imputed as 0.749 (\log_{10} TCID₅₀/mL).

Only patients with a positive virus titer on Day 1 will be included in this analysis.

Change from baseline in the amount of virus RNA (RT-PCR) at each timepoint

Change from baseline in the amount of virus RNA (unit: \log_{10} virus particles/mL) is defined as the change from baseline in the amount of virus RNA on Days 2, 3, 4, 5, 7, and 10 and will be analyzed using an ANCOVA model with region (North America, EMEA, ROW), NEWS2 (≤ 7 , > 7), and time from symptom onset to study treatment (≤ 48 hours, > 48 hours) as stratification variables, and the baseline value as a covariate.

If the amount of virus RNA is less than the lower limit of quantification, the amount of virus RNA will be imputed as 2.18 for flu A and 2.93 for flu B (\log_{10} virus particles/mL). If a patient is infected with multiple virus types, the sum of those amounts of virus RNA will be used for analysis.

Patients with a positive by RT-PCR on Day 1 will be included in this analysis.

Proportion of patients with positive influenza virus titer

Proportion of patients positive for influenza virus titer will be presented by treatment at each visit and is defined as the percentage of patients whose influenza virus titer is not less than the lower limit of quantification (0.75 \log_{10} TCID₅₀/mL) or positive among those

assessed for influenza virus titer on Days 2, 3, 4, 5, 7, and 10. The Cochran-Mantel-Haenszel test with region (North America, EMEA, ROW), NEWS2 at baseline (≤ 7 , > 7), and time from symptom onset to study treatment (≤ 48 hours, > 48 hours) as stratification variables, and the baseline value as a covariate will be used to compare proportion of patients positive for influenza virus titer between treatments at each scheduled time point.

Patients with a positive influenza virus titer on Day 1 will be included in this analysis.

Proportion of patients positive by RT-PCR at each time-point

Proportion of patients positive by RT-PCR will be presented by treatment at each visit is defined as the percentage of patients with detectable virus RNA (2.05 for flu A and 2.83 for flu B log₁₀ virus particles/mL) among those assessed by RT-PCR on Days 2, 3, 4, 5, 7, and 10. The Cochran-Mantel-Haenszel test with region (North America, EMEA, ROW), NEWS2 at baseline (≤ 7 , > 7), and time from symptom onset to study treatment (≤ 48 hours, > 48 hours) as stratification variables, and the baseline value as a covariate will be used to compare proportion of patients positive by RT-PCR between treatments at each scheduled time point.

Patients with a positive by RT-PCR on Day 1 will be included in this analysis.

Area under the curve in virus titer

Area under the curve (AUC) in virus titer will be presented by treatment group and will be calculated using the trapezoidal method. AUC of change from time 0 (t_0) to time K (t_k) is given by the formula:

$$\sum_{k=1}^K \frac{(y_k + y_{k-1})(t_k - t_{k-1})}{2}$$

where t_k (hours) represents the date of the k th viral titer assessment ($k = 0, \dots, K$) and y_k represents the log₁₀ value of the k th viral titer assessment (TCID₅₀/mL). 24-hours of time will be converted into one day. Patients with a positive virus titer on Day 1 will be subjected to this analysis. The lower limit of quantification and lower limit of detection is defined as 0.75 log₁₀ TCID₅₀/mL for flu A and 0.75 log₁₀ TCID₅₀/mL for flu B (TCID₅₀/mL). If a patient is infected with multiple virus types, the sum of those virus titers will be used for analysis.

Additionally, the AUC in virus titer adjusted for baseline will be presented by treatment group and be calculated using the trapezoidal method. AUC of change from time 0 (t_0) to time K (t_k) adjusted for baseline is given by the formula:

$$\sum_{k=1}^K \frac{(y_k + y_{k-1} - 2y_0)(t_k - t_{k-1})}{2}$$

where t_k (hours) represents the date of the k^{th} viral titer assessment ($k = 0, \dots, K$) and y_k represents the \log_{10} value of the k^{th} viral titer assessment (TCID₅₀/mL). 24-hours of time will be converted into one day. Patients with a positive virus titer on Day 1 will be subjected to this analysis. The lower limit of quantification and lower limit of detection is defined as $0.75 \log_{10}$ TCID₅₀/mL for flu A and $0.75 \log_{10}$ TCID₅₀/mL for flu B (TCID₅₀/mL). If a patient is infected with multiple virus types, the sum of those virus titers will be used for analysis.

Area under the curve in the amount of virus RNA (RT-PCR)

AUC in virus RNA (RT-PCR) will be presented by treatment group and is defined as AUC of change from baseline in the amount of virus RNA (RT-PCR) from Day 1 to Day 10. AUC is calculated using the trapezoidal method similar to AUC in virus titer.

Patients with a positive RT-PCR result on Day 1 will be subjected to this analysis. The lower limit of quantification is defined as 2.18 for flu A and 2.93 for flu B (\log_{10} virus particles/mL). If a patient is infected with multiple virus types, the sum of those the amount of virus RNA will be used for analysis.

Exposure and virology will be included in the pop PK report.

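### For patients with more than one influenza type, the SAP sums virus RNA amounts that it defines in log10 units; read as written this multiplies the loads and exaggerates the fall from baseline

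*SAP*

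**What the plan says.** All the relevant text is in SAP 4.6.

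- **RNA change from baseline.** The definition, which opens "Change from baseline in the amount of virus RNA (unit: \log_{10} virus particles/mL) is defined as the change from baseline in the amount of virus", puts the endpoint in a log10 unit. For unquantifiable results the text reads: "the amount of virus RNA will be imputed as 2.18 for flu A and 2.93 for flu B (\log_{10} virus particles/mL"). The multi-type rule follows directly: "If a patient is infected with multiple virus types, the sum of those amounts of virus RNA will be used for analysis". The analysis is an ANCOVA with the baseline value as covariate.
- **RNA AUC.** This is the area under the change from baseline, Day 1 to Day 10. The quantification limits are again given in log10, and the rule is repeated: "If a patient is infected with multiple virus types, the sum of those the amount of virus RNA will be used for analysis".
- **Titre AUC.** The quantity integrated, y_k, is the log10 value of the titre assessment. The rule is: "If a patient is infected with multiple virus types, the sum of those virus titers will be used for analysis". Both an unadjusted and a baseline-adjusted AUC are presented.
- **Titre change from baseline.** There is no rule for multiple types.
- **Time to cessation by RT-PCR.** No sum is used. The event is the "first time when the virus RNA by RT-PCR is below the limit of detection for all virus types".

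Neither document says that values are back-transformed before they are summed.

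**The concern.** A sum of log10 values is the log10 of the product of the loads, not of their total. The RNA text attaches log10 to the amount itself, in both the unit and the imputed values, so the natural reading of the next sentence is that these log10 figures are added.

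Under that reading a patient with two types is measured on a different scale from everyone else. The change from baseline becomes the sum of the two type-specific log reductions, and the ANCOVA covariate becomes the sum of two log baselines. That makes the patient a possible outlier in the response and a high-leverage point in the covariate. Protocol 4.1.1 admits influenza A and/or B, and SAP 4.6 writes several multi-type rules, so such patients are foreseen.

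Two programmers working from the same text could also obtain different values for the same patient.

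**Working it through.** The plan gives no combined figure for a multi-type patient, so there is nothing to reproduce. The check compares the rule as written with summation on the natural scale.

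**Inputs from SAP 4.6.** RNA imputation 2.18 (A) and 2.93 (B); RT-PCR detection limits 2.05 (A) and 2.83 (B); titre imputation 0.749, given under titre change from baseline. All are log10. **Inputs from SAP 2.4.** 264 mITTI patients, 176 on baloxavir and 88 on placebo. **Assumed.** Baseline loads, and the number of patients with both types.

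**1. Level when both types are unquantifiable.**
- As written: 2.18 + 2.93 = 5.11, i.e. 10^5.11 = 128,825 particles/mL.
- Natural scale: log10(10^2.18 + 10^2.93) = log10(151.4 + 851.1) = log10(1,002.5) = 3.00.
- Difference: 2.11 log10, a factor of 128,825 / 1,002.5 = about 128.5.

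Both detection limits lie below the corresponding imputed values, so a patient who has cleared both types receives 5.11. So does one who is detectable but not quantifiable in both.

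**2. Change from baseline, both types falling below quantification.** As written: 5.11 - (a + b). Natural scale: 3.00 - log10(10^a + 10^b).

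| Assumed baseline A / B | Summed logs | Change as written | log10 of total | Change, natural scale | Ratio |
|---|---|---|---|---|---|
| 7 / 6 | 13 | -7.89 | 7.04 | -4.04 | 1.95 |
| 6 / 5 | 11 | -5.89 | 6.04 | -3.04 | 1.94 |
| 5 / 5 | 10 | -4.89 | 5.30 | -2.30 | 2.13 |
| 7 / 3.5 | 10.5 | -5.39 | 7.00 | -4.00 | 1.35 |

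The first row shows the mechanism. Type A falls by 7 - 2.18 = 4.82 and type B by 6 - 2.93 = 3.07; the rule adds these to 7.89, although the total load fell by only 4.04. The exaggeration depends on the two baselines and is 1.35 to 2.13 times in these examples, which are illustrations and not limits.

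**3. Titre AUC, if logs are summed.** Two types at the floor give 2 x 0.749 = 1.498, against log10(2 x 10^0.749) = 0.749 + 0.301 = 1.05.

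**4. Effect on an arm mean.** Take the first row, with an excess of 7.89 - 4.04 = 3.85 log10 per patient, and assume 5 co-infected patients among 264 (about 2%):
- spread in proportion to arm size: 5 x 3.85 / 264 = 0.07 in each arm;
- all on baloxavir: 5 x 3.85 / 176 = 0.11;
- all on placebo: 5 x 3.85 / 88 = 0.22.

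The first case leaves the unadjusted difference between arms essentially unchanged. The RNA analyses include only patients positive on Day 1, so the true denominators may be smaller and the shift per patient somewhat larger.

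**The case against.** The multi-type sentences never name a scale, so a sensible programmer could add loads in particles/mL and then take log10. For the titre AUC this objection stands. The text distinguishes the titre from y_k, its log10 value, so a sum of titres can be read as a natural-scale sum that is logged afterwards. Against that, the titre change-from-baseline text imputes the titre directly in log10. A reader might infer that the titre AUC certainly adds logs; the wording does not settle it.

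For RNA the objection is weaker. The amount is given a log10 unit, the sentence immediately before the rule imputes that amount in log10, and the rule refers back to those amounts. Even if natural-scale summation was intended, the text does not say so.

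A second tempting inference is that a cleared patient would look heavily infected at 5.11 log10. The RNA endpoints do not support this. They analyse change, so 5.11 is subtracted from an even more inflated baseline and the patient looks unusually well cleared. Only the unadjusted titre AUC uses levels, and its floor would be 1.498, not 5.11. Whether a patient counts as negative by RT-PCR depends on detection limits, not on the sum.

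It can also fairly be said that the consequence is small. The virology endpoints are outside the test sequence in SAP 4.5. The only link to the primary endpoint is the descriptive TTCI subgroup in SAP 4.5.4 split at the median titre AUC, where rank matters and the size of an outlier does not.

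**Conclusion.** The point holds for RNA. As written, the rule in the change-from-baseline and AUC text of SAP 4.6 gives a wrong combined value for a patient with more than one type and overstates that patient's decline. For the titre AUC the finding is an ambiguity of scale, not a demonstrated error.

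The figure of 5.11 against 3.00 follows from the SAP's own imputation values and applies to A with B. If two influenza A viruses were counted as separate types, the figures would be 2 x 2.18 = 4.36 against 2.18 + 0.301 = 2.48. The changes from baseline rest on assumed baselines, so a general statement that the change is doubled would go too far. The arm-mean shift of 0.07 to 0.22 log10 rests on one baseline pair, full clearance at the visit analysed, and five co-infected patients. The documents give no co-infection rate, and with none the effect is zero.

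A reader might infer that the trial's efficacy conclusions are at risk. They are not: the primary test, both key secondary endpoints and time to cessation of shedding do not use the sum. This is a minor correction that prevents outlying values in secondary virology analyses.

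**What to change.** In SAP 4.6, under RNA change from baseline, RNA AUC and titre AUC, state that for patients with multiple virus types the type-specific loads are summed on the natural scale after imputation and then log10-transformed: log10(10^A + 10^B), with A and B the log10 values for the two types.

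As an addition rather than a correction, apply the same rule to titre change from baseline, which at present has no multi-type rule. It would also help to say whether two influenza A subtypes count as multiple types.

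The cost is one sentence in each place and one line of code. Sample size, testing order and trial procedures do not change, and no result changes for patients with a single type.
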